10.1.6 Other analysis sets

For duration of MMR and time to MMR, the MMR Responder Set will be used that includes patients who achieve MMR at any time.

For CCyR rates at and by scheduled time points, the CCyR Analysis Set will be used that includes patients who are not in CCyR at baseline.

For duration of CCyR and time to CCyR, the Cytogenetic Responder Set will be use that includes patients who do not have CCyR at baseline and achieve CCyR at any time.

10.2 Patient demographics/other baseline characteristics

Demographic and other baseline data including disease characteristics will be listed and summarized descriptively by treatment group for the FAS or the Safety Set.

Categorical data will be presented as frequencies and percentages. For continuous data, mean, standard deviation, median, minimum, and maximum will be presented.

[figure not shown]
Relevant medical histories and current medical conditions at baseline will be summarized separately by system organ class and preferred term, by treatment group.

10.3 Treatments (study treatment, concomitant therapies, compliance)

The Safety set will be used for the analyses below.

Categorical data will be summarized as frequencies and percentages. For continuous data, mean, standard deviation, median, 25th and 75th percentiles, minimum, and maximum will be presented.

The duration of exposure in days to ABL001 and bosutinib, as well as the dose intensity (computed as the ratio of actual cumulative dose received and actual duration of exposure)

and the relative dose intensity (computed as the ratio of dose intensity and planned dose intensity) will be summarized by means of descriptive statistics.

The number of patients with dose adjustments (reductions, interruption, or permanent discontinuation) and the reasons will be summarized by treatment group and all dosing data will be listed.

Concomitant medications and significant non-drug therapies prior to and after the start of the study treatment will be listed and summarized according to the Anatomical Therapeutic Chemical (ATC) classification system, by treatment group.

10.4 Primary objective

The primary objective of the study is to evaluate the efficacy of ABL001 at the recommended dose in CML patients in chronic phase, previously treated with 2 or more tyrosine kinase inhibitors and to compare this efficacy profile in this population with that achieved by patients receiving bosutinib.

10.4.1 Variable

The primary efficacy variable of the study is the Major Molecular Response (MMR) rate at 24 weeks. A patient will be counted as having achieved MMR at 24 weeks if he meets the MMR criteria (BCR-ABL ratio $\leq 0.1\%$) at 24 weeks.

10.4.2 Statistical hypothesis, model, and method of analysis

The MMR rate at 24 weeks will be calculated based on the FAS and according to the Intent To Treat (ITT) principle. MMR rate and its 95% confidence interval based on the Pearson-Clopper method will be presented by treatment group. The confidence interval for the difference in MMR rate between treatment groups will be provided using the Wald method.

The null hypothesis is that there is no difference between the treatment groups with respect to MMR rate at 24 weeks. The Cochran-Mantel-Haenszel chi-square test, stratified by the randomization stratification factor, i.e. major cytogenetic response status (PCyR or CCyR vs others) at screening, will be used to compare MMR rate between the two treatment groups, at the two-sided 5% level of significance. The Mantel-Haenszel estimate of the common risk difference and the corresponding 95% confidence interval will also be provided.

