10.6.1.1 Data analysis of exploratory efficacy objectives

Subgroup analyses will be performed to evaluate the influence of factors such as baseline major cytogenetic response status, baseline BCR-ABL ATP-binding site mutation status (from local historical record and from Sanger Sequencing), failure/intolerance to prior TKIs, line of therapy, gender, race and age on the primary efficacy endpoint. In addition, a logistic regression analysis will incorporate the key baseline variables into the model to further evaluate the impact of these variables on the primary endpoint and to provide a treatment effect estimate which is adjusted for imbalances in the treatment groups. An adjusted odds ratio for the treatment effect with associated 95% confidence intervals will be presented. Mantel-Haenszel estimates of the common odds ratio and the corresponding 95% confidence interval will also be provided.

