10.8 Sample size calculation

To test the null hypothesis that the response rate is equal in the two groups, based on two-sided 5% level of significance and with 90% power, 222 patients will be needed in total (i.e. 148 patients in the ABL001 arm and 74 patients in the bosutinib arm based on 2:1 randomization allocation). This assumes that ABL001 leads to a 20% improvement in the MMR rate at 24 weeks over bosutinib from 15% to 35% which corresponds to an odds ratio of 3.05.

The assumed bosutinib MMR rate of 15% at 24 weeks is based on previous trials evaluating bosutinib therapy ([Khoury 2012](#), [Gambacorti-Passerini 2014](#), [García-Gutiérrez 2015](#)).

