4.1 Description of study design

The study is a phase 3, multi-center, open-label randomized study of oral asciminib versus bosutinib in patients with Chronic Myelogenous Leukemia in chronic phase (CML-CP), previously treated with 2 or more tyrosine kinase inhibitors.

The trial is designed to compare the efficacy and safety of asciminib with that of bosutinib in the treatment of patients with CML-CP having previously been treated with a minimum of two prior ATP-binding site TKIs. Patients intolerant to the most recent TKI therapy must have BCR-ABL1 ratio $> 0.1\%$ IS at screening and patients failing their most recent TKI therapy must meet the definition of treatment failure as per the 2013 ELN guidelines ([Baccarani et al 2013](#)). No more than 66 patients (approximately 30% of the overall trial population) that are intolerant to their most recent TKI therapy with BCR-ABL1 $< 1\%$ will be recruited in order to ensure that the CML third line patient population is adequately represented.

The study will also investigate secondary endpoints for efficacy, safety and PK of single-agent asciminib compared to bosutinib. Tolerability, PK, PRO and exploratory biomarker activities will also be assessed. Safety and efficacy data for patients switching to asciminib will be collected and analyzed separately.

Patients meeting all of the inclusion and none of the exclusion criteria will be randomized into one of the 2 treatment arms, based on a 2:1 randomization between the asciminib arm and the bosutinib arm.

[figure not shown]
The randomization will be stratified to ensure the study population is balanced between the arms with respect to cytogenetic response status (See [Section 7.2.1.2](#)) at screening as follows:

- Major cytogenetic response (complete or partial)
- No major cytogenetic response (minor, minimal or none)

Patients will continue to receive the assigned study treatments (asciminib or bosutinib) until the end of study treatment period as defined in [Section 4.3](#). Patients who discontinue their study treatment at any time during the study will be followed up for survival and for progression to AP/BC for up to 5 years from the date the last randomized patient receives the first dose (irrespective of treatment switch for patients failing bosutinib).

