6.6.2 Treatment assignment or randomization

Patients will be assigned to one of the 2 treatment arms (Section 4.1 and Section 6.1) in a ratio of 2:1. Randomization will be stratified by cytogenetic response status at screening.

The randomization numbers will be generated using the following procedure to ensure that treatment assignment is unbiased and concealed from patients and investigator staff. A patient randomization list will be produced by the Interactive Response Technology (IRT) provider using a validated system that automates the random assignment of patient numbers to randomization numbers. These randomization numbers are linked to the different treatment arms, which in turn are linked to medication numbers. A separate medication randomization list will be produced by or under the responsibility of Novartis Drug Supply Management using a validated system that automates the random assignment of medication numbers to medication packs containing each of the study treatments.

[figure not shown]
Prior to dosing, all patients who fulfill all inclusion/exclusion criteria will be randomized via IRT to one of the treatment arms. The investigator or his/her delegate will call or log on to the IRT and confirm that the patient fulfills all the inclusion/exclusion criteria. The IRT will assign a randomization number to the patient, which will be used to link the patient to a treatment arm and will specify a unique medication number for the first package of study treatment to be dispensed to the patient. The randomization number will not be communicated to the caller.

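### The Week 24 CMH test adjusts only for cytogenetic response, not screening BCR-ABL1; Amendment 3 widens the entry range, so check and, if unchanged, update the adjustment and stated power

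*Combined protocol and SAP*

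**What the plan says.** The supplied text holds two protocol versions: Amendment 1 (10-Apr-2017) in full, and Amendment 3 (14-Dec-2018) up to Section 7.1.2.

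**Amendment 1**
- Section 5.2 requires BCR-ABL of at least 1% IS for everyone. Section 10.4.1 defines response as a ratio of at most 0.1% at Week 24.
- Section 10.4.2 tests the primary endpoint with "The Cochran-Mantel-Haenszel chi-square test, stratified by the randomization stratification factor, i.e. major cytogenetic response status (PCyR or CCyR vs others) at screening". Section 10.5.1.1 does the same at Week 96.
- Section 10.8 states that "based on two-sided 5% level of significance and with 90% power, 222 patients will be needed in total", split as "148 patients in the ABL001 arm and 74 patients in the bosutinib arm based on 2:1 randomization allocation", for an "improvement in the MMR rate at 24 weeks over bosutinib from 15% to 35% which corresponds to an odds ratio of 3.05".
- Section 10.6.1.1: "Subgroup analyses will be performed to evaluate the influence of factors such as baseline major cytogenetic response status". The list continues with mutation status, failure or intolerance, line of therapy, gender, race and age. BCR-ABL level is not named. A supportive logistic regression uses key baseline variables that are not listed.

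**Amendment 3**
- Section 5.2, criterion 3a, lowers the threshold to >0.1% IS for patients intolerant to their last TKI. Section 4.1 adds a cap: "No more than 66 patients (approximately 30% of the overall trial population) that are intolerant to their most recent TKI therapy with BCR-ABL1" below 1%.
- Section 5.1 keeps 222 patients. Section 6.6.2: "Randomization will be stratified by cytogenetic response status at screening".
- Section 7.1.2 requires the RQ-PCR result before randomisation.
- The change list names 10.1.6, 10.4.3, 10.5.1.1, 10.5.2, 10.5.3.1 and parts of 10.6. It names neither 10.4.2 nor 10.8, and the amendment rationale gives no revised response rates.

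**The concern.** Because the endpoint is a threshold on BCR-ABL1, the screening value measures how far each patient has to travel to become a responder. A patient entering at 0.2% needs a two-fold fall and one at 20% needs a 200-fold fall. MCyR status captures this only partly, since patients below 1% can share a stratum with partial cytogenetic responders at higher levels.

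Under the ≥1% rule every patient started at least ten-fold above the threshold. Amendment 3 removes that floor for intolerant patients. If the analysis and power text were not revisited, three things follow. Precision available from a value already collected is left unused. A chance imbalance in a likely strong prognostic factor passes into the primary estimate. And the 90% power statement describes a population defined by a superseded entry criterion.

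**Working it through.** **1. The plan's own figure.** Inputs from Section 10.8: 15% vs 35%, two-sided 5%, 148 vs 74. Pooled two-proportion formula without continuity correction:

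power = Φ{ [ |pA − pB| − 1.96·√(p̄(1−p̄)(1/148 + 1/74)) ] / √(pA(1−pA)/148 + pB(1−pB)/74) }

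p̄ = (148×0.35 + 74×0.15)/222 = 0.283. The pooled SE is 0.0642 and the unpooled SE 0.0571. Power = Φ{(0.200 − 0.1257)/0.0571} = Φ(1.30) = 90.3%. Solving for N at 90% gives 74 + 148 = 222. The odds ratio is (0.35/0.65)/(0.15/0.85) = 3.05. The stated figures reproduce exactly.

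**2. Size of the new group.** 66/222 = 29.7%. The Amendment 3 rationale reports 86 randomised by 21-Nov-2018, leaving about 136. If the cap is filled, 66/136 = 49% of later entrants could be in this group.

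**3. Power with 66 low-burden patients.** The documents give no MMR rate for patients entering at >0.1% to <1%, so the subset rates are assumptions. The other 156 patients keep 15%/35%. Example with the subset at 50% vs 70%:
- pB = (156×0.15 + 66×0.50)/222 = 0.254
- pA = (156×0.35 + 66×0.70)/222 = 0.454
- power = Φ{(0.200 − 1.96×0.0694)/0.0651} = Φ(0.98) = 84%

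| Assumed subset rate on bosutinib | Difference stays 20 points | Odds ratio stays 3.05 | Difference 10 points |
|---|---|---|---|
| 20% | 89% | 92% | 78% |
| 25% | 88% | 92% | 77% |
| 35% | 86% | 92% | 74% |
| 50% | 84% | 89% | 71% |
| 60% | 83% | 85% | 69% |

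In the 20-point column, N for 90% power runs from 228 to 276. The cap is a ceiling: at 50% vs 70%, 22, 44 and 66 such patients give 88%, 86% and 84%.

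**4. What adjustment recovers.** Simulated trials (4,000 per scenario, N = 222, 2:1 blocks within MCyR, 66 patients below 1%) compared CMH strata of MCyR alone with MCyR × (<1% vs ≥1%). MCyR was assumed in 90% of low-burden and 30% of other patients, or in 70% and 50%. Each cell gives results in that order.

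| Subset rates (others 15%/35%) | MCyR only | MCyR × BCR-ABL1 |
|---|---|---|
| 35% vs 55% | 86%, 86% | 87%, 87% |
| 50% vs 70% | 85%, 84% | 88%, 88% |
| 50% vs 60% | 72%, 71% | 75%, 75% |

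The gain is about 1 to 4 points. A three-level split (<1%, 1–10%, >10%) under other assumed rates gave about 5 points (86% to 91% and 74% to 79%). Those scenarios do not keep 15%/35% in patients at ≥1%, so only the gain, not the power level, is informative.

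**5. Type I error.** With equal arms (subset 50% or 60%, others 15%), the MCyR-only test rejected in 4.4–5.5% of runs. The Monte Carlo standard error is √(0.05×0.95/4000) = 0.34 points, so this is consistent with 5%.

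**The case against.** The strongest objection concerns versions. Sections 10.4.2, 10.6.1.1 and 10.8 as supplied date from Amendment 1, when entry required ≥1%. They cannot show what the amended plan does. A reader might infer that the sponsor changed the population and left the analysis and power untouched. The documents do not establish that. The unchanged N, the unchanged stratum and the change list make it a reasonable inference, but Amendment 3 has its own Section 10, which is not supplied, and it lists 10.6.1.1 among the revised sections. This stands, so the check must come first.

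Second, Section 10.6.1.1 already plans a logistic regression adjusted for baseline imbalance, its subgroup list is open-ended, and MCyR is correlated with disease burden. This stands in part: a route exists, but the most relevant variable is not named in it.

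Third, testing by the randomisation factor is a valid prespecified choice, and changing the primary test of an open-label trial after 86 randomisations has its own cost. MCyR × three categories would also be sparse. If 35% of patients were above 10% and 15% of those had MCyR, the cell would hold 222×0.35×0.15 ≈ 12 patients, about 4 on bosutinib. This stands. It favours a two-level split and makes a named sensitivity analysis an acceptable minimum.

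Fourth, the new patients need not be close to the threshold: >0.1% to <1% spans a ten-fold range. This also stands.

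**Conclusion.** The point holds as a matter of precision, chance imbalance and an accurate power statement. Screening BCR-ABL1 is collected before randomisation and bears directly on the endpoint, yet the supplied Section 10 does not use it by name. Amendment 3 makes the omission matter more, provided its own Section 10 and any SAP prove unchanged.

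Two stronger readings are not supported. One is that the primary test is invalid: simulated type I error is near 5%. The other is that power has certainly fallen below 90%: it may rise slightly, to about 92%, if the subset odds ratio stays 3.05 and its bosutinib rate is 20–35%. The lowest values (69–78%) require the subset difference to halve to 10 points. Every subset rate is an assumption, and all figures use a full 66 patients.

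The number below 1% could also exceed 66. The cap covers intolerant patients only, and criterion 3a sets no BCR-ABL1 floor for patients entering on failure, although the Amendment 3 summary still carries the ≥1% wording.

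**What to change.** First check Amendment 3 Sections 10.4.2, 10.6.1.1 and 10.8, and any SAP. If they are unchanged, then before analysis:

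1. Prespecify a CMH test and Mantel-Haenszel risk difference stratified by MCyR and screening BCR-ABL1 (<1% vs ≥1% IS), with a preset rule for collapsing sparse cells. Make it the primary analysis or, at minimum, a named sensitivity analysis, at both Week 24 and Week 96.
2. Name screening BCR-ABL1 as a covariate in the supportive logistic model and as a subgroup factor.
3. Restate the Section 10.8 power as a range for the amended case mix, labelling subset rates as assumptions and including both the constant-difference and constant-odds-ratio cases.

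The cost is SAP wording and minor programming. No new data, visits or change to randomisation are needed. The downside is smaller strata and a possibly less favourable stated power.

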10.4.3 Handling of missing values/censoring/discontinuations

Only patients with MMR at 24 weeks are considered responders. In other words, any patient who achieves MMR before 24 weeks, but is no longer in MMR at 24 weeks, will be considered as a non-responder in this primary analysis. Patients discontinuing the randomized treatment prior to 24 weeks due to any reason will be considered as non-responders.

One exception to the rule above is if the 24-week PCR evaluation is missing, but both a PCR evaluation at 16 weeks and a PCR evaluation at 36 weeks indicate MMR, the 24-week assessment is imputed as a 'Response'.

10.4.4 Supportive and Sensitivity analyses

The analysis of the primary endpoint will also be repeated on the PPS if the PPS is different from the FAS.

Subgroup analyses and a logistic regression analysis will be employed. Refer to the exploratory objectives [Section 10.6.1](#) for further details.

10.5 Secondary objectives

The secondary objectives in this study are as follows:

- To compare additional parameters of the efficacy of ABL001 versus bosutinib, defined as:

Key secondary endpoints

[figure not shown]
- MMR rate at 96 weeks

Other efficacy endpoints

- Cytogenetic response (Complete, Partial, Major, Minor, Minimal, no response) rate at all scheduled data collection time points including 24, 48 and 96 weeks.
 - Cytogenetic response (Complete, Partial, Major, Minor, Minimal, no response) rate by all scheduled data collection time points including, 24, 48 and 96 weeks.
 - MMR rate at all scheduled data collection time points (except 24 and 96 weeks which are already covered by primary and key secondary endpoints)
 - MMR rate by all scheduled data collection time points including 24, 48 and 96 weeks.
 - Time to MMR
 - Duration of MMR
 - Time to CCyR
 - Duration of CCyR
 - Time to treatment failure
 - Progression free survival
 - Overall survival
-
- To compare the safety and tolerability profile of ABL001 versus bosutinib
 - To characterize the PK of ABL001 in the CML-CP population

10.5.1 Key secondary objective(s)

The key secondary endpoint to be evaluated is MMR rate at 96 weeks, which is defined as the proportion of patients with MMR at 96 weeks and derived in a similar fashion to MMR rate at 24 weeks.

10.5.1.1 Analysis for key secondary objectives

The null hypothesis is that there is no difference between the treatment groups with respect to MMR rate at 96 weeks. Formal statistical testing of the key secondary endpoint will be performed with $\alpha = 0.05$ (two-sided) only if the primary endpoint is significant by means of a gatekeeping procedure to control the overall alpha level.

MMR rate at 96 weeks will be evaluated in a similar fashion to the primary analysis of MMR rate at 24 weeks. The rate and the associated 95% confidence interval based on the Pearson-Clopper method will be presented by treatment group. Confidence interval for the difference between treatment groups will be provided using the Wald method.

Statistical testing will be performed via CMH chi-square test stratified by the randomization strata. The Mantel-Haenszel estimate of the common risk difference and the corresponding 95% confidence interval will also be provided.

10.5.2 Other secondary efficacy objectives

Unless otherwise stated the FAS will be used for the analysis of all other secondary efficacy endpoints. The exceptions are using the Molecular Responder Set for duration of MMR and time to MMR, the CCyR Analysis Set for CCyR rates, and the Cytogenetic Responder Set for duration of CCyR and time to CCyR.

No statistical testing of non-key secondary efficacy endpoints will be performed, however a nominal p-value will be presented for exploratory purposes.

Molecular Response

MMR rates at scheduled time points (except 24 and 96 weeks which have been specified as primary and key secondary endpoints) will be evaluated in a similar fashion to the primary analysis of MMR rate at 24 weeks. Patients discontinuing the randomized treatment prior to a specific time point due to any reason will be considered as non-responders for that time point.

MMR rates by scheduled time points are defined as the proportion of patients who achieve MMR at or before the specified visit, i.e. if a patient achieves an MMR but then loses it before or at the visit, he/she will still be classed as achieving MMR by that time point.

For each endpoint the rate and the associated 95% confidence interval based on the Pearson-Clopper method will be presented by treatment group. Confidence intervals for the differences in any response rates between treatment groups will be provided using the Wald method.

Statistical testing will be performed via CMH chi-square tests stratified by the randomization strata. The Mantel-Haenszel estimate of the common risk difference and the corresponding 95% confidence interval will also be provided.

Duration of MMR is defined in [Section 7.2.1.1](#) as the time between the date of the first documented MMR and the earliest date of loss of MMR, progression to AP/BC, or CML-related death for patients in the Molecular Responder Set. The time will be censored at the last molecular assessment (PCR) date on treatment for patients who have not experienced any of the above events.

Duration of MMR will be analyzed by K-M method and presented by K-M plots. The estimated rates of patients who are still responding at various time points will also be provided using K-M method.

The cumulative incidence of MMR will be graphically displayed by an increasing step function. This curve will increase each time (after randomization) at which a new responder is observed and thus will increase up to the best observed response rate (e.g. up to 50% if half of the patients in the analysis population are able to achieve response).

Time to MMR is defined in [Section 7.2.1.1](#) as: date of first MMR - date of randomization +1, for patients in the Molecular Responder Set. Descriptive statistics (range, median, quartiles, mean, sd) of time to MMR will be provided for the two treatment groups separately.

Cytogenetic Response

Patients in FAS will be categorized with counts and percentages provided for cytogenetic response (Complete, Partial, Major, Minor, Minimal, No Response) at and by (i.e. best response up to a specified time point) scheduled time points. Shift tables will also be employed to examine the changes in cytogenetic response category from baseline.

Since there are expected to be only very limited numbers who are actually in CCyR at baseline (due to the inclusion criteria requiring BCR-ABL ratio $\geq 1\%$) the analysis of CCyR rate at and by scheduled time points will only include patients who are not in CCyR at baseline, i.e. the CCyR Analysis Set.

CCyR rates at and by scheduled time points etc. and the associated 95% confidence intervals based on the Pearson-Clopper method will be presented by treatment group with the analysis of these endpoints only including patients who are not in CCyR at baseline.

Confidence intervals for the differences in any response rates between treatment groups will be provided using the Wald method.

Statistical testing will be performed via CMH chi-square tests stratified by the randomization strata. The Mantel-Haenszel estimate of the common risk difference and the corresponding 95% confidence interval will also be provided.

Time to CCyR is defined for patients in the Cytogenetic Responder Set as: date of first CCyR - date of randomization +1. Descriptive statistics (range, median, quartiles, mean, sd) of time to CCyR will be provided for the two treatment groups separately.

The cumulative incidence of CCyR will also be graphically displayed by an increasing step function. This curve will increase each time (after randomization) at which a new responder is observed and thus will increase up to the best observed response rate.

Duration of CCyR is defined as the time between date of first documented CCyR and the earliest date of loss of CCyR, progression to AP/BC, or CML-related death for patients in the Cytogenetic Responder Set. The time will be censored at the last cytogenetic assessment date on treatment for patients for whom none of the above events is reported or last PCR evaluation on treatment indicating MMR.

Duration of CCyR response will be analyzed by K-M method and presented by K-M plots. The estimated rates of patients who are still responding at various time points will also be provided using K-M method.

Treatment failure, disease progression and survival

Time to treatment failure (TTF) is defined as the time from date of randomization to an event of treatment failure. The following events will constitute ‘treatment failure’, and are based on the ELN criteria ([Bacarrani 2013](#)) defining failure of a second line treatment adapted to include discontinuation of randomized treatment as an event:

- No CHR or > 95% Ph+ metaphases at three months after randomization or thereafter
- BCR-ABL ratio > 10% IS and/or > 65% Ph+ metaphases at six months after randomization or thereafter
- BCR-ABL ratio > 10% IS and/or > 35% Ph+ metaphases at 12 months after randomization or thereafter
- Loss of CHR, CCyR or PCyR at any time after randomization
- Detection of new BCR-ABL mutations at any time after randomization
- Confirmed loss of MMR in 2 consecutive tests, of which one must have a BCR-ABL ratio $\geq 1\%$ IS 6 months after randomization
- New clonal chromosome abnormalities in Ph+ cells: CCA/Ph+: at any time after randomization
- Discontinuation from randomized treatment for any reason

For patients who have not reach treatment failure, their TTFs will be censored at the time of last study assessment (PCR, cytogenetic, hematologic or extramedullary).

Progression-Free-Survival (PFS) is defined as the time from the date of randomization to the earliest occurrence of documented disease progression to AP/BC or the date of death from any cause (including progressions and deaths observed during the survival follow-up period).

The time will be censored at the date of last study assessment (PCR, cytogenetic, hematologic or extramedullary) or last post-treatment follow-up for patients without event.

Overall survival (OS) is defined as the time from the date of randomization to the date of death (including the survival follow-up period). Patients who are alive at the time of the analysis data cutoff date will be censored at the date of last contact before the cut-off date.

TTF, PFS and OS will be estimated and graphically displayed using the K-M approach. The estimated rates by K-M method at various time points will be provided and the endpoints will be compared between the two treatment groups using stratified log-rank test stratified by the randomization strata. The hazard ratio and 95% confidence intervals will be computed from a stratified Cox model.

